9.3 Number of patients

Under the above assumptions (see 9.1), total accrual to the controlled phase of this trial is planned for 200 patients. The sample size calculation accounts for loss to follow-up in 1/4 of recruited patients (i.e. 54 patients) within 24 months.

9.4 Efficacy

Evaluation of bone marrow aspirate, peripheral blood counts and differentials are used to assess the efficacy of the study medication.

Response criteria

Response criteria are defined according to the Revised Recommendations of the International Working Group for Diagnosis, Standardization of Response Criteria, Treatment Outcomes, and Reporting Standards for Therapeutic Trials in Acute Myeloid Leukemia [12].

Morphologic leukemia-free state:

- Bone marrow (aspirate with marrow spicules): < 5% blasts, absence of Auer rods
- No evidence of persisting leukemia by flow cytometry (Sensitivity: 5%)
- Absence of extramedullary leukemia
- Peripheral blood with no blast cells and either less than $1,000/\mu l$ granulocytes and/or less than $100,000/\mu l$ platelets

Morphologic Complete Response (CR):

- Platelet count $> 100,000/\mu l$
- Granulocyte count of >1,000/μ1
- Bone marrow (aspirate with marrow spicules): < 5% blasts, absence of Auer rods
- No evidence of persisting leukemia by flow cytometry (Sensitivity: 5%)
- Absence of extramedullary leukemia
- Transfusion independent stable hemoglobin value

Cytogenetic Complete Response (CRc):

- Platelet count >100,000/µl
- Granulocyte count of >1,000/μl

- Bone marrow (aspirate with marrow spicules): < 5% blasts, absence of Auer rods
- No evidence of persisting leukemia by flow cytometry (Sensitivity: 5%)
- Absence of extramedullary leukemia
- Transfusion independent stable hemoglobin value
- Reversion to normal karyotype (based on conventional banded studies and FISH)

Molecular Complete Response (CRm):

- Platelet count >100,000/µl
- Granulocyte count of >1,000/µl
- Bone marrow (aspirate with marrow spicules): < 5% blasts, Absence of Auer rods
- No evidence of persisting leukemia by flow cytometry (Sensitivity: 5%)
- Absence of extramedullary leukemia
- Transfusion independent hemoglobin value
- Normal cytogenetics (based on conventional banded studies and FISH)
- Molecularly negative (no detection of pre-treatment genetic markers with a methodology providing a sensitivity of at least 1:10³)

Partial Remission (PR):

- Platelet count >100,000/µl
- Granulocyte count of >1,000/µl
- Bone marrow (aspirate with marrow spicules): Decrease of bone marrow blast percentage to 5% 25% and decrease of pretreatment bone marrow blast percentage by at least 50%

Death in Aplasia:

• Death occurring ≥ 7 days following completion of initial chemotherapy (CT); death while cytopenic, with aplastic bone marrow and without evidence of persisting leukemia

Death from indeterminate cause:

Death occurring before completion of therapy, or < 7 days post CT; Patients who die ≥ 7 days post CT with no PB blasts, but bone marrow examination not performed or not evaluable; Patients who do not complete the first course of therapy

Morphologic relapse:

• Reappearance of blasts post CT in PB or \geq 5% blasts in the bone marrow or development

of extramedullary disease

In addition to these response criteria, incomplete CR (CRi) is defined as:

CR with incomplete recovery (CRi) with neutrophils < 1,000/µl and platelets < 100,000/µl

Treatment failure is defined as:

no morphologic leukemia-free state, no partial remission

In addition, early treatment response at day 15 after start of first induction chemotherapy is defined

as:

Good response: < 5% blasts

Poor response: $\geq 5\%$ blasts

9.5 **Definition of Study Endpoints**

Event free survival (EFS):

Time interval from day 1 of study treatment until treatment failure, relapse from CR or CRi,

or death from any cause, whichever occurs first. The time point at which the patient is

resistant to therapy or survives induction without a CR, CRi or morphologic leukemia-free

state will be recorded.

For a patient with none of these events before the end of study follow-up, observation of EFS

will be censored at the date of his or her last follow-up examination.

Relapse free survival (RFS):

Time interval from the day of documentation of CR until relapse or death from any cause.

Overall survival (OS):

Time interval from day 1 of study treatment to the day of death. For a patient who is not

known to have died by the end of follow-up, observation of OS will be censored on the date

the patient was last known to be alive.

Study protocol, TOR-AML, Final Version 3.1, April 13rd, 2012

63

Complete remission rate (CR rate):

The proportion of patients in complete remission (CR, as defined above) after induction chemotherapy.

Early response rate:

The proportion of patients with a morphologic leukemia-free state (as defined above, < 5% blasts) in the first treatment assessment on day 15 after start of first induction chemotherapy.

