4.3.2.2 Secondary objectives

- to compare the median Event Free Survival (EFS) of AML patients with different cytogenetic and molecular risk groups¹
- to compare the rate of early response (< 5 % bone marrow blasts on d15) after the first induction cycle between the temsirolimus and the control group
- to compare the rate of early response after the first induction cycle of AML patients with different cytogenetic and molecular risk groups¹
- to compare the Complete Remission (CR) rate of the temsirolimus with the control group
- to compare the CR rate of AML patients with different cytogenetic and molecular risk groups¹
- to compare Relapse Free Survival (RFS) of AML patients between the temsirolimus and the control group
- to compare Relapse Free Survival (RFS) of AML patients with different cytogenetic and molecular risk groups¹
- to compare the Overall Survival (OS) of all AML patients between the temsirolimus and the control group
- to compare the Overall Survival (OS) of AML patients with different cytogenetic and molecular risk groups¹
- to compare the rate of molecular remissions of the temsirolimus with the control group
- to compare the toxicity of the temsirolimus and the control treatment
- to compare the rate of molecular relapse after molecular remission of all AML patients between the temsirolimus and the control group after induction therapy and in the course of the first remission
- to evaluate potential biomarkers indicating the course of disease, including genetic, epigenetic, transcriptional and protein markers as well as indicators of autophagy in leukemic blasts, bone marrow, peripheral blood cells, serum and plasma

* EFS defined as: Time interval from day 1 of study treatment until treatment failure, relapse from CR or CRi, or death from any cause, whichever occurs first. The time point at which the patient is resistant to therapy or survives induction without a CR, CRi or morphologic leukemia-free state will be recorded.

¹Cytogenetic and molecular risk groups (13)

Favorable t(8;21)(q22;q22); RUNX1-RUNX1T1

inv(16)(p13.1q22) or t(16;16)(p13.1;q22); CBFB-MYH11

Mutated *NPM1* without *FLT3*-ITD (normal karyotype)

Mutated CEBPA (normal karyotype)

Intermediate-I* Mutated *NPM1* and *FLT3*-ITD (normal karyotype)

Wild-type *NPM1* and *FLT3*-ITD (normal karyotype)

Wild-type *NPM1* without *FLT3*-ITD (normal karyotype)

Intermediate-II t(9;11)(p22;q23); MLLT3-MLL

Cytogenetic abnormalities not classified as favorable or adverse

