6.3.2.5 Consolidation therapy I and II

All patients in CR/CRi should receive **two cycles of consolidation chemotherapy**, if conditions described below are fulfilled.

Precondition for consolidation therapy:

CR/CRi with neutrophils $> 1000/\mu l$ and platelets $> 75,000/\mu l$ up to 42 days after last chemotherapy

- Start of consolidation therapy not earlier than one week and not later than 2
 weeks after confirmation of CR
- If patients' condition does not allow for immediate consolidation chemotherapy it may be postponed for up to 4 weeks after confirmation of CR/CRi
- If patients' condition does not allow for consolidation chemotherapy within 4 weeks from confirmation of CR: Maintenance therapy should be started (arm A) or observation (arm B)

No CRi with neutrophils $> 1000/\mu l$ and platelets $> 75,000/\mu l$ at 35 - 42 days after last chemotherapy

 Bone marrow evaluation should be performed between day 35 and 42 to exclude relapse

CRi with neutrophils $> 1,000/\mu l$ and platelets $> 75,000/\mu l$ between day 43 and day 59

• Reduction dose of temsirolimus / placebo should be considered in the forthcoming cycles (for dose reduction see section 5.3.4).

No CRi with neutrophils $> 1,000/\mu l$ and platelets $> 75,000/\mu l$ by day 54 - 60

- Bone marrow evaluation should be considered after day 54 in order to exclude relapse
- Patients may proceed directly to maintenance therapy (arm A) or observation (arm B). The decision is made by the investigator.

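### The response categories behind the confirmatory EFS endpoint contradict each other: read literally, 9.4 makes complete remission a treatment failure, and PR, CRi and regrowth from a leukemia-free state have no settled place

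*Protocol*

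**What the plan says.** Protocol 9.2 makes the stratified log-rank comparison of EFS the confirmatory analysis. In 9.5, in the footnote to 4.3.2.2 and in the synopsis, EFS runs from day 1 of study treatment "until treatment failure, relapse from CR or CRi, or death from any cause, whichever occurs first". The next sentence in each place says that the time will be recorded at which a patient is resistant or comes through induction without reaching any of CR, CRi or MLFS.

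Section 9.4 defines the categories:

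- **Treatment failure:** "no morphologic leukemia-free state, no partial remission". CR and CRi are not mentioned and no time point is given.
- **MLFS:** under 5% blasts plus a blood-count condition, "Peripheral blood with no blast cells and either less than" 1,000/µl granulocytes and/or under 100,000/µl platelets.
- **CR:** under 5% blasts, granulocytes above 1,000/µl, platelets above 100,000/µl, transfusion-independent hemoglobin.
- **PR:** 5% to 25% blasts with at least a halving, and the same recovered counts as CR.
- **CRi:** "CR with incomplete recovery (CRi) with neutrophils < 1,000/µl and platelets < 100,000/µl".

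Elsewhere the same terms differ. The day-15 rule in 6.3.1.3, 6.3.2.3 and the synopsis uses the same failure wording, but its MLFS has no count condition and neither does its PR. Section 6.3.2.5 and the synopsis work with CRi at neutrophils above 1,000/µl and platelets above 75,000/µl.

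**The concern.** Treatment failure is a component of the primary endpoint, so its definition has to sort every patient into event or no event. In 9.4 it is written as the absence of two categories, and CR belongs to neither. The rule works on day 15, where MLFS carries no count limit. It stops working in 9.4, where MLFS does carry one.

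Three further cases depend on the same wording: a patient left in PR after induction, a patient whose remission has one low count, and a patient whose blasts return after MLFS but before CR or CRi. For each, the sections point in different directions or are silent. Whoever programs EFS must override the text, and the protocol does not say which override to use. The choice decides whether such a patient has an event at a marrow examination, at a later death, or not at all within follow-up.

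**Working it through.** **1. The planned sample size, for reference.** Inputs from 9.1: medians 7 and 11.75 months, two-sided 0.05, power 80%, 1:1 allocation, 24 months accrual, 12 months follow-up.

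- Hazard ratio = 7/11.75 = 0.596.
- Schoenfeld events = 4 × (1.960 + 0.842)² / (ln 0.596)², rounded up = 118.
- Event probability per arm, exponential with uniform accrual: 1 − (e^(−12λ) − e^(−36λ)) / (24λ), with λ = ln 2/median. This gives 0.884 (control) and 0.736 (temsirolimus), mean 0.810.
- 118/0.810 = 145.7, so 146 evaluable. With 54 of 200 (27%) not evaluable, 146/0.73 = 200.

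The plan's figures reproduce. Nothing below changes them.

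**2. The written rules applied to example records.** The check assumes 60% blasts before treatment, no Auer rods, no peripheral blasts or extramedullary disease, and transfusion independence. Records show marrow blasts / granulocytes / platelets per µl.

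| Record | 9.4 category | Failure by 9.4? | Failure by day-15 rule? | Accepted state in 9.5? |
|---|---|---|---|---|
| 2% / 2,000 / 150,000 | CR | **yes** | no | yes |
| 2% / 2,000 / 80,000 | MLFS; not CR, not CRi | no | no | yes |
| 2% / 500 / 150,000 | MLFS; not CR, not CRi | no | no | yes |
| 2% / 500 / 50,000 | MLFS, and meets CRi counts | no | no | yes |
| 15% / 2,000 / 150,000 | PR | no | no | **no** |
| 15% / 2,000 / 80,000 | none | yes | no | no |
| 50% / any counts | none | yes | yes | no |

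**3. CR (first row).** CR needs both counts above the limits and MLFS needs at least one below, so no patient is both. PR needs 5% blasts or more and CR needs fewer. Every CR patient therefore meets the written failure rule in 9.4, against 9.5 and the day-15 rule.

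**4. PR (fifth row).** Under 9.4 a patient left in PR after induction is not a failure. Under 9.5 the same patient has come through induction without CR, CRi or MLFS. On the first reading there is no event at that point. On the second the event falls at the post-induction assessment.

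**5. CRi.** Section 9.4 requires neutrophils below 1,000/µl; 6.3.2.5 and the synopsis require them above 1,000/µl. No patient meets both. The second-row patient is CRi by the counts in 6.3.2.5 and can go on to consolidation, but by 9.4 is only MLFS. Unless counts later reach CR, a relapse in this patient is not from CR or CRi as 9.4 defines them.

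**6. Regrowth from MLFS.** It is not a listed EFS event. Treatment failure carries no time point, however, so a later marrow can be scored against it:

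- MLFS with both counts low also meets the CRi counts in 9.4, so regrowth can count as relapse from CRi.
- For patients without recovered counts, 6.3.2.5 says: "Bone marrow evaluation should be performed between day 35 and 42 to exclude" relapse. Such patients have neutrophils no higher than 1,000/µl or platelets no higher than 75,000/µl, so they cannot be PR, which needs more than 1,000 and more than 100,000. With 5% blasts or more they are neither MLFS nor PR, and are failures at that marrow.
- What remains is mainly MLFS with a single low count that regrows to 5% to 25% blasts with recovered counts. That meets PR, so it is not a failure, and it is not a relapse from CR or CRi.

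**The case against.** The strongest reply is that the adjacent text answers the CR problem. The second EFS sentence in 9.5 accepts CR. Listing relapse from CR as a later event would be pointless if CR were itself an event. The failure phrase repeats the day-15 rule, and the early-response definition in 9.5 glosses MLFS simply as under 5% blasts. All of this stands: CR was not meant to be a failure, and a sensible analyst would not code it so.

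A reader might therefore take the literal wording too far. With the approximately 50% CR rate in section 3, one could infer that about 100 of 200 patients would be mislabelled and that median EFS would fall to the end of induction. The documents do not support that as a forecast. It follows only if 9.4 is read alone, and it cannot be squared with the 7-month control median in 9.1.

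A reader might also infer that every patient cleared on day 15 whose blasts return before CR or CRi has EFS dated at death. That needs failure to be scored on day 15 only, which no section states. The CR problem, in turn, arises only if the 9.4 categories are applied to a later assessment. The two problems cannot both be pressed at full strength under one scoring rule.

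What the reply does not remove is that the protocol never says which scoring rule applies. Nor does it resolve PR or the two CRi definitions. These are definitions that the protocol itself states in conflicting forms, not detail left to an analysis plan.

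**Conclusion.** The point holds as a contradiction among stated definitions of a primary-endpoint component. Three parts are certain from the text: 9.4 taken literally classes CR as treatment failure, against 9.5 and the day-15 rule; PR after induction is treated differently by 9.4 and 9.5; and CRi has two count definitions that exclude each other. A fourth part is narrower: regrowth from MLFS is not a listed event, but most of it could be scored as failure at the marrow that shows it. The clear residue is mainly single-low-count MLFS regrowing to a state that meets PR.

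I attach no number of patients and no loss of power. The protocol gives neither the share in MLFS on day 15 nor the share that regrows before CR or CRi, so any figure would rest on assumption alone. The sample size is not in question.

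**What to change.** Change endpoint wording only. The treatment rules in 6.3 can stay as the sponsor sets them, provided that the terms they share with 9.4 are reconciled or clearly separated from endpoint scoring.

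- Use one MLFS and one CRi definition for endpoint scoring. This also settles the early response rate in 9.5, which refers back to MLFS.
- In 9.4 and 9.5, define treatment failure for EFS as none of CR, CRi or MLFS at a stated post-induction assessment. CR is then safely outside failure, and PR is handled as the second sentence of 9.5 implies. Merely adding CR and CRi to the existing exemptions while keeping PR would preserve the conflict with 9.5.
- In 9.5, the 4.3.2.2 footnote and the synopsis, extend the relapse component to relapse from CR, CRi or MLFS, dated at the marrow that shows it.

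The cost is an amendment to wording in those four places. The counts and marrow findings needed are those that the CR rate already requires, and the 146 evaluable and 200 total patients stay as planned.

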6.3.2.3 Decision making on second induction

Bone marrow will be analyzed on day 15:

In case of **morphologic leukemia-free state** (< 5% blasts in an aspirate, no blasts in peripheral blood and no extramedullary disease), no second induction chemotherapy is given. In case of **partial remission** (decrease of bone marrow blast percentage to 5% - 25% and decrease of pretreatment bone marrow blast percentage by at least 50%) or **treatment failure** (no morphologic leukemia-free state, no partial remission), a (second) induction cycle with HAM (elderly) + temsirolimus/placebo will be administered on day 22 of first induction chemotherapy if possible.

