6.3.2.4 Treatment schedule for induction II chemotherapy

HAM (elderly) induction II for patients with PR or treatment failure:

HD-AraC	1g/m ² (2 x daily)	infusion over 3 hours	day 1, 3, 5
Mitoxantrone	10mg/m^2	infusion over 30-60 minutes	day 3-5
Temsirolimus /Placebo	25mg abs.	infusion over 30-60 minutes	day -1 and +8

If the duration of the aplasia exceeds 42 days the dose of temsirolimus/placebo should be reduced according to the dose reduction scheme (5.3.5) in these patients for the following temsirolimus/placebo applications.

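### The primary EFS event treatment failure is defined inconsistently: its only definition has no assessment time, repeats the day-15 trigger for the planned second induction, and leaves out partial remission after induction

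*Protocol*

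**What the plan says.** - **EFS** (Protocol 4.3.2.2 footnote, 9.5, synopsis): "Time interval from day 1 of study treatment until treatment failure, relapse from CR or CRi, or death from any cause, whichever occurs first". The following sentence says that the time point at which a patient is resistant or "survives induction without a CR, CRi or morphologic leukemia-free state will be recorded".
- **Treatment failure** (9.4): "no morphologic leukemia-free state, no partial remission". This is the only definition, and it gives no assessment time.
- **Day-15 decision** (6.3.2.3, repeated in the synopsis): "Bone marrow will be analyzed on day 15". Patients in PR or in treatment failure go on to a second course: "no morphologic leukemia-free state, no partial remission), a (second) induction cycle with HAM (elderly) + temsirolimus/placebo will be administered on day 22". Section 6.3.2.4 titles that course "HAM (elderly) induction II for patients with PR or treatment failure".
- **Partial remission**: 9.4 requires platelets above 100,000/µl and granulocytes above 1,000/µl as well as the blast criteria. Section 6.3.2.3 uses the blast criteria alone.
- **Leukemia-free state**: 9.4 requires granulocytes below 1,000/µl and/or platelets below 100,000/µl. Section 6.3.2.3 has no count requirement.
- **Transplantation** (9.2): EFS is censored at allogeneic transplantation.

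**The concern.** One term does two jobs. In 6.3.2.3 it is an interim marrow category, and the patients in it continue on protocol induction. In 9.5 it is a terminal event of the confirmatory endpoint, and the first event counts. Nothing in 9.4 or 9.5 separates the two uses.

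The definition also excludes PR, while the next EFS sentence groups a patient who survives induction in PR with the non-responders. At stake is who has an event and when. Two analysts following this text could build different EFS data sets, and the choice could be made after the data are known.

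**Working it through.** **1. The definitions applied to four patients**

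- *Day-15 failure, then CR after the planned second course.* The 9.4 wording is met on day 15. With the first event counting, EFS ends at about day 15. Under the second EFS sentence the patient has not failed, because induction ended in CR.
- *PR after the last induction course.* This is not treatment failure under 9.4. There is no CR or CRi to relapse from, so only death counts. If the patient is transplanted, 9.2 censors EFS and the induction failure may never be an event. The second EFS sentence groups this patient with the non-responders but only records the time point.
- *Full CR.* With recovered counts the patient is outside the 9.4 leukemia-free state. With blasts below 5% the patient is outside PR. Both halves of the failure wording are therefore met.
- *Leukemia-free state, then relapse without a documented CR or CRi.* Relapse is an EFS event only from CR or CRi, so the relapse does not count.

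**2. The two PR definitions**

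Section 8.12.1.1 expects grade IV hematological toxicity after induction. A day-15 patient with 5% to 25% blasts and at least a 50% reduction is in PR under 6.3.2.3, but usually not under 9.4. Using 9.4 throughout enlarges the first group above and shrinks the second. Using the blast-only version does the reverse.

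**3. The plan's own sample size (9.1)**

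Inputs: medians of 7 and 11.75 months, two-sided α = 0.05, power 80%, 1:1 allocation, 24 months' accrual, 12 months' follow-up. Exponential EFS and uniform accrual are assumed.

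- HR = 7/11.75 = 0.596; ln HR = −0.518.
- Events (Schoenfeld) = 4 × (1.960 + 0.842)² / 0.518² = 117.03, rounded up to 118.
- Event probability = 1 − [exp(−λ·12) − exp(−λ·36)] / (24λ), with λ = ln 2 / median. This gives 0.884 (control) and 0.736 (temsirolimus), mean 0.810.
- Patients = 118 / 0.810 = 145.7, rounded up to 146.

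The stated 146 is reproduced, so the sample-size arithmetic is not at fault.

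**4. Illustration of early misdating**

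The protocol gives no day-15 failure rate and no CR rate after the second course. Assume 15% to 35% day-15 failure and CR in 30% to 50% of those. The share q given a false early event is then 0.15 × 0.30 = 4.5% to 0.35 × 0.50 = 17.5%. Let q be equal in both arms, date these events at 0.5 month, and leave all other patients on the design's exponential curves. The shifted median is −(m / ln 2) × ln[0.5 / (1 − q)]. Power comes from simulated log-rank tests with 146 patients.

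| q | Medians (months) | Power |
|---|---|---|
| 0 | 7.0 / 11.75 | 80% |
| 5% | 6.5 / 10.9 | 75% |
| 10% | 5.9 / 10.0 | 70–71% |
| 17.5% | 5.1 / 8.5 | 63–65% |

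Ranges are across separate simulation runs. Expected events rise only from 118 to about 123. The added events do not differ between arms and dilute the contrast.

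**The case against.** The strongest reply is that end of induction was plainly meant. No section says that EFS is read on day 15. Section 9.4 has its own day-15 classification, good or poor response, separate from treatment failure. The second course is named induction II, so surviving induction without response naturally refers to the end of one or two courses, with PR as failure. Section 7.4 lists treatment failure beside relapse as a point after which survival is followed. On that reading the first two anomalies disappear, and the analysis plan may set the date.

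Much of this stands: the intention is probably as described. But the second EFS sentence only records a time point. It does not make it the event or its date, and it contradicts the stated definition on PR. An analysis plan that followed one sentence would depart from the other.

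A reader might also infer stronger claims that the documents do not support:

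- *That the trial will in fact misdate a known share of EFS times.* The misdating follows from the literal text only, and every rate used to size it is assumed. The early-event and PR groups also move in opposite directions with the choice of PR definition, so they cannot simply be added.
- *That nearly all day-15 non-responders become failures.* Section 6.3.2.3 has its own blast-only PR for that decision.
- *That the 7-month control median belongs to a different endpoint.* Section 3 takes the control EFS from an earlier trial of the same group. Its EFS definition is not shown and may be the same.
- *That one arm is favoured.* The wording is common to both arms and induction is blinded. The harm is to power and interpretation.

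**Conclusion.** The point holds as an inconsistency in the definition of the confirmatory endpoint, and it should be corrected before analysis. Three things are firm from the text: the failure definition has no assessment time and duplicates the day-15 category; PR after induction is handled in two incompatible ways; and the wording, taken with the 9.4 criteria for leukemia-free state, is met even by a full CR.

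The size is not derivable from the protocol. A fall in power from 80% to roughly 75% to 65% rests on assumed shares of 5% to 17.5%, equal in both arms. It also adds early events to curves whose 7-month median may already include induction failures. It shows that the choice of reading can matter; it is not an estimate of what will happen.

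**What to change.** Reconcile the EFS text (4.3.2.2 footnote, 9.5, synopsis), the day-15 wording (6.3.2.3, synopsis) and the response criteria (9.4):

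1. For EFS, define induction failure once: no CR, CRi or leukemia-free state after completed protocol induction, whether one course or two. PR at that point is then a failure.
2. State the event date, using response assessments already made.
3. Give the day-15 category a different name and state that it is not itself an EFS event.
4. Use one PR definition for the endpoint.
5. State how relapse from leukemia-free state without a documented CR or CRi is counted.

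The clinical rule for giving a second course does not change.

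The cost is a wording amendment, carried into the analysis plan. One limit remains. The 7.2 schedule has no routine marrow at day 35–42 after the last induction course; 6.3.2.5 asks for one in that window only where CRi with the required counts has not been reached. Failure dates will therefore depend on when the post-induction marrow is taken, and the dating rule should say so.
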